10.2.5 SAEs (Including Deaths) and Adverse Events Leading to Study Drug Discontinuation

SAEs (including deaths) and AEs leading to study drug discontinuation will be summarized by SOC and PT and in listing format.

In addition, the event rate per 100 patient-years of exposure will also be provided by SOC and PT for each treatment-emergent SAE and TEAE leading to study drug discontinuation.

10.2.6 Adverse Events of Special Interest

Adverse Events of Special Interest (AESI, formerly known as Safety topics of interest) will be summarized by SOC and PT and will be based on standardized or company MedDRA queries (SMQs or CMQs), or based on adjudication results. AESIs to be summarized will follow those indicated in the latest version of the Product Safety Statistical Analysis Plan (PSSAP) for ABBV-154 in the AESI/Safety Topics of Interest section. Detailed information about search criteria for the AESIs are also provided in a table in the same section.

Tabular listings of AESIs will be provided.

In addition, the event rate per 100 patient-years of exposure will also be provided by SOC and PT for each AESI.

10.3 Analysis of Laboratory Data

Data collected from central and local laboratories, including additional laboratory testing due to an SAE, will be used in all analyses, except for Baseline where SAE-related laboratory assessments on or before the first dose of study drug will be excluded. The clinical laboratory tests defined in the protocol operations manual (e.g., hematology and clinical chemistry) will be summarized.

Each laboratory variable will be summarized for all time points (starting with Baseline) with the number of non-missing observations, mean and standard deviation, median, minimum and maximum. Mean change from baseline to each applicable post-baseline visit will be summarized for selected laboratory variables, with the number of observations, baseline mean, and visit mean. The change from baseline mean, standard error, and 95% confidence interval will be presented for the mean change from baseline within each treatment group and difference between treatment groups (ABBV-154 vs. placebo) as applicable. This summary and change from baseline summary will be presented once by treatment sequence.

Changes in laboratory parameters will be tabulated using shift tables either by NCI CTC criteria or other criteria listed in Appendix B. A shift table from baseline either to the worse value (based on NCI CTC criteria) during treatment or to minimum and maximum value (based on normal range), will be created. A similar shift table will be provided to summarize shifts from baseline to the final post-baseline value.

Laboratory abnormalities meeting CTC criteria grade 3 and 4 will be summarized.

Laboratory abnormalities will be evaluated based on Potentially Clinically Important (PCI) criteria (based on NCI CTC criteria, except for those listed in Appendix B). For each laboratory PCI criterion, the number and percentage of subjects who have a laboratory value meeting the criteria will be summarized. Listings will be provided to summarize subject-level laboratory data for subjects meeting PCI criteria. In the evaluation of PCI laboratory values, the baseline value for the ALL_154 population will

be determined by the last non-missing measurement recorded on or before the date of the first dose of study drug in the corresponding ABBV-154 treatment group (which may be different than the first dose of study drug received in the study).

For the purpose of assessing for potential Hy's law cases, the frequencies and percentages of subjects with post baseline liver specific function test values that meet the following criteria of potential clinical interest will be summarized by "as treated" treatment group:

- $ALT > 3 \times ULN$
- $ALT > 5 \times ULN$
- $ALT > 10 \times ULN$
- $ALT > 20 \times ULN$
- $AST > 3 \times ULN$
- $AST > 5 \times ULN$
- $AST > 10 \times ULN$
- $AST > 20 \times ULN$
- $TBL > 2 \times ULN$
- Alkaline phosphatase $> 1.5 \times ULN$
- ALT and/or $AST > 3 \times ULN$ and concurrent $INR > 1.5$
- ALT and/or $AST > 3 \times ULN$ and concurrent $TBL > 2 \times ULN$

A listing of possible Hy's Law cases, defined as those who meet all of the following conditions simultaneously, will be provided: $ALT > 3 \times ULN$ or $AST > 3 \times ULN$ that is associated with an increase in bilirubin $> 2 \times ULN$.

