2.3 Treatment Assignment and Blinding

Subjects will remain on a stable dose of MTX until Week 24 (unless qualifying for rescue therapy as described in Protocol Section 5.4); thereafter MTX may be adjusted within the range of 7.5 – 25 mg/week. At Baseline, approximately 425 subjects will be randomized to 5 treatment groups in a 1:1:1:1:1 ratio to receive ABBV-154: 40 mg, 150 mg, 340 mg SC EOW; 340 mg SC E4W, or placebo. Randomization will be stratified by Baseline glucocorticoid (yes/no); number of prior failed b/tsDMARDs (1; 2 or more); and prior anti-TNF failure (yes/no) and if yes further stratification by prior adalimumab use (yes/no). At Week 12, subjects assigned to placebo will be re-randomized in a 1:1 ratio to receive ABBV-154 150 mg or 340 mg SC EOW; subjects from the other dose groups will continue with their respective dose and dosing regimen. Re-randomization will be stratified by Baseline glucocorticoid use (yes/no) and prior adalimumab use (yes/no). The

enrollment for subjects with prior adalimumab use is capped at approximately 30% of the total subjects enrolled. Systemic glucocorticoids (dose of ≤ 7.5 mg/d prednisone equivalent at Baseline) must be tapered off within 4 weeks of the start of study drug.

All AbbVie personnel with direct oversight of the conduct and management of the trial (except for AbbVie Drug Supply Management Team) will be blinded to each subject's treatment through Week 12. The AbbVie study team will be unblinded to treatment assignment for the Primary Analysis. This unblinding will take place after all subjects have completed the Week 12 visit or have withdrawn from the study prior to Week 12. To maintain integrity of the trial, the study site personnel and the subjects will remain blinded until all subjects have either completed the last visit of LTE Period 1 or have withdrawn from the study. Blinded dosing regimens will be continued until the previous criteria are met. To maintain the blind, the ABBV-154 and placebo pre-filled syringes provided for the study will be identical in appearance. The IRT will provide access to unblinded subject treatment information in the case of a medical emergency.

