2.4 Sample Size Determination

The planned total sample size of 425 subjects (approximately 85 subjects per treatment group) provides at least 90% power to detect a 22% difference between ABBV-154 and placebo in ACR50 response rate at Week 12 (assuming a placebo ACR50 response rate of 13%), at a 2-sided significance level of 0.1 based on Chi-square test.

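### Between-arm differences in laboratory and vital-sign change are planned without baseline as a covariate, and SAE-driven laboratory tests can enter post-baseline by-visit means: a loss of precision, not a bias

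*SAP*

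**What the plan says.** SAP 10.3 sets the laboratory data rule: "Data collected from central and local laboratories, including additional laboratory testing due to an SAE, will be used in all analyses". The only exception concerns the reference value, where results prompted by an SAE up to the first dose are left out. The section then plans by-visit mean changes for selected laboratory variables, with a standard error and 95% interval within each group and for the "difference between treatment groups (ABBV-154 vs. placebo) as applicable". SAP 10.4 plans the same output for each vital sign but has no clause on SAE-driven measurements.

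Neither section names a model or a covariate. SAP 10.3 does not say which result represents a visit when a scheduled and an SAE-driven result both exist. By contrast, the mixed model for continuous efficacy endpoints in SAP 9.2.3 includes the baseline measurement as a covariate. Protocol 7.5 gives mean change a descriptive role and leaves the detail of the safety analysis to the SAP.

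SAP 10.3 also plans medians, minima and maxima of the values at each time point, shift tables, Grade 3 and 4 summaries, PCI counts and listings, and liver-test thresholds up to 20 x ULN.

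**The concern.** Safety and tolerability are part of the primary objective (Protocol 3.1), and limited systemic exposure to the glucocorticoid payload is the product's rationale (Protocol 2.1). Placebo subjects move to ABBV-154 at Week 12 (SAP 2.3), so the first 12 weeks are the only placebo-controlled comparison. A modest average shift in HbA1c, potassium, lipids, blood pressure or weight would show in the mean-change tables rather than in tables that count threshold crossings.

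Two features weaken those tables. A covariate that is already collected goes unused. In addition, a post-baseline laboratory mean may contain results taken because of an acute event, whereas the baseline mean may not. Such a result describes the event, which the AE, shift and PCI outputs already report. In a mean it adds noise, and the wider interval could hide a real average shift.

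**Working it through.** **Inputs.** SAP 2.4: "The planned total sample size of 425 subjects (approximately 85 subjects per treatment group"), so n = 85 per arm. SAP 2.3: subjects are "randomized to 5 treatment groups in a 1:1:1:1:1 ratio". The correlation r between baseline and follow-up, the equal standard deviations in step 2, and the values in steps 3 and 4 are assumptions; the documents give none of them.

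**1. The plan's own figure.** The only power statement concerns ACR50: the sample size "provides at least 90% power to detect a 22% difference between ABBV-154 and placebo in ACR50 response rate at Week 12". Its assumptions are 13% response on placebo, a two-sided alpha of 0.1 and a chi-square comparison. With rates of 0.13 and 0.35 (mean 0.24):

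z = [0.22 x √85 − 1.645 x √(2 x 0.24 x 0.76)] / √(0.13 x 0.87 + 0.35 x 0.65) = (2.028 − 0.993) / 0.584 = 1.77, so power is 96.2%.

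The stated minimum of 90% is met, and n = 85 is a sound basis for what follows. No power or precision is stated for laboratory or vital-sign change.

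**2. Cost of leaving out the covariate.** Let s be the common standard deviation at baseline and follow-up.

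- Variance of the difference in raw change: 2s²(1 − r) x 2/n.
- Variance of the ANCOVA difference: s²(1 − r²) x 2/n.
- Ratio: 2/(1 + r). The interval widens by √(2/(1 + r)) − 1. The unadjusted n per arm that matches 85 adjusted is 85 x 2/(1 + r).

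| Assumed r | Variance ratio | Interval wider by | Unadjusted n matching 85 adjusted |
|---|---|---|---|
| 0.3 | 1.54 | 24.0% | 130.8 |
| 0.5 | 1.33 | 15.5% | 113.3 |
| 0.7 | 1.18 | 8.5% | 100.0 |
| 0.9 | 1.05 | 2.6% | 89.5 |

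The direction does not depend on equal standard deviations. With s0 at baseline and s1 at follow-up, the per-subject variance of change minus the ANCOVA residual variance is (s0² + s1² − 2r·s0·s1) − s1²(1 − r²) = (s0 − r·s1)², which is never negative.

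**3. One SAE-driven value in an arm mean.** A result that differs by d from the rest of the arm moves the arm mean by d/n. For an illustrative ALT of 1,000 U/L against a baseline of 25, the shift is (1,000 − 25)/85 = 11.5 U/L.

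In ULN units, assume a baseline of 0.6 x ULN, a standard deviation of change of 0.3 x ULN, and no mean change in the other subjects. The standard error of the difference without the value is 0.3 x √(2/85) = 0.046.

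| ALT (x ULN) | Shift in arm mean (x ULN) | Shift / SE without the value | SE with the value (x ULN) | Shift / SE with the value |
|---|---|---|---|---|
| 5 | 4.4/85 = 0.052 | 1.1 | 0.069 | 0.75 |
| 10 | 9.4/85 = 0.111 | 2.4 | 0.120 | 0.92 |
| 20 | 19.4/85 = 0.228 | 5.0 | 0.233 | 0.98 |

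With a standard deviation of 0.2 to 0.5 x ULN, the 20 x ULN shift is 7.4 to 3.0 times the standard error without the value.

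**4. Can one value create significance?** No. The value adds d²(n − 1)/n to the arm's sum of squares, and so d²/n² to the squared standard error. That is the square of the shift itself, and the other subjects' variance comes on top. The shift is therefore always less than one standard error of the reported difference. The practical effect is a displaced estimate and a wider interval: in the 20 x ULN case the standard error rises from 0.046 to 0.233, about fivefold.

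**The case against.** The strongest defence is that these are descriptive tables. No test is attached, the unadjusted difference in change is unbiased under randomization, and at high correlation the gain from adjustment is only a few percent. The SAP names no model at all, so the lack of adjustment is inferred from silence. The plan already has medians, shift tables, Grade 3 and 4 summaries, PCI counts, liver thresholds and listings, as well as AESI tables, glucocorticoid adjudication and DXA. Whether an SAE-driven result reaches a visit mean depends on a visit-value rule that SAP 10.3 does not state. Restricting means to central results would discard legitimate data, since Protocol 8.2 allows a local laboratory to replace the central one in a crisis.

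Much of this stands, and it caps the importance of the point. It does not remove it. The threshold tables find individual extremes, not modest average shifts, and they do not repair the interval around the mean difference. The planned medians are of values, and no median change is planned. The missing visit-value rule is itself a reason to add a sentence. The objection to a central-only rule is right, and the fix keeps scheduled local substitutes.

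A reader might go further and infer that baseline is ignored, or that the comparison is biased. The documents do not support either: a change score subtracts baseline, and the exclusion of SAE tests from Baseline applies equally to all arms. A reader might also infer that every efficacy change is adjusted while safety is not. The As Observed long-term summaries in SAP 9.2.4 are not adjusted either.

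**Conclusion.** The point holds as a minor, optional improvement to descriptive safety tables. Without baseline as a covariate, the intervals for the between-arm differences in SAP 10.3 and 10.4 are about 15.5%, 8.5% and 2.6% wider at an assumed correlation of 0.5, 0.7 and 0.9. These percentages assume equal standard deviations at the two visits. Only precision is lost.

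The SAE clause concerns laboratory data alone and does not touch blood pressure or weight. It covers central as well as local tests, so it should not be read as a problem of local laboratories. Taken literally, it lets one extreme result move an 85-subject arm mean (11.5 U/L in the ALT illustration) and inflate its standard error. It would be wrong to conclude that one subject could produce an apparently significant difference: the shift stays below one standard error of the reported difference. The example uses ALT; no comparable shift has been calculated for the glucocorticoid-related measures. The primary efficacy conclusion is not affected.

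**What to change.** Amend SAP 10.3 and 10.4 as follows.

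- For the Placebo-Controlled Period, compute each ABBV-154 minus placebo difference in laboratory and vital-sign change by ANCOVA with the baseline value as covariate. This uses data already collected and is a free gain in precision.
- Base laboratory by-visit means and mean changes on scheduled samples, using the central result where available and keeping scheduled local results that replace it.
- Keep all SAE-driven and local laboratory values in the shift, CTC grade, PCI and liver tables, so that no event is hidden.

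The cost is a few sentences in the SAP and one small loss: where the only result at a visit is SAE-driven, that subject drops out of that visit's mean. The result still appears in the extreme-value outputs.

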10.4 Analysis of Vital Signs

Vital sign measurements of systolic and diastolic blood pressure, respiratory rate, pulse rate, and body temperature will be summarized. Weight will be included in the summaries.

Each vital sign variable will be summarized for all time points (starting with Baseline) with the number of non-missing observations, mean and standard deviation, median, minimum and maximum. Mean change from baseline to each applicable post-baseline visit will be summarized for each vital sign variable, with the number of observations, baseline mean, and visit mean. The change from baseline mean, standard error, and 95% confidence interval will be presented for the mean change from baseline within each treatment group and difference between treatment groups (ABBV-154 vs. placebo) as applicable. This summary and change from baseline summary will be presented once by treatment sequence.

Vital sign variables will be evaluated based on PCI criteria. Pulse rate, body temperature, and respiratory rate will follow the criteria in Appendix B. All other vital signs will follow the criteria in the PSSAP. For each vital sign PCI criterion, the number and percentage of subjects who have a vital sign value meeting the criteria will be summarized. Listings will be provided to summarize subject-level vital sign data for subjects meeting PCI criteria. In the evaluation of PCI vital sign values for the ALL_154 population, the baseline value will be determined by the last non-missing measurement recorded on or before the date of the first dose of study drug in the corresponding ABBV-154 treatment group.

10.5 Safety Subgroup Analyses

The AE Overview and AE by SOC and PT summaries will be provided for the stratification variables:

- Baseline glucocorticoid dose (yes/no)
- Number of prior failed b/tsDMARDs (1; 2 or more)

10.6 Other Safety Analyses

ECG is collected at screening, Week 12, Week 24, Week 36, Week 78, Week 134, and Week 182. ECG findings will be summarized by treatment group for each parameter and visit.

Dual-energy X-ray absorptimetry (DXA) is collected at screening, Week 24, Week 78, Week 134, and Week 182. DXA measurements, including bone mineral density and corresponding T and Z scores, will be summarized by treatment group for each visit and also in the following groups:

- Female patients' post-menopausal status at baseline (Yes/No)
- Bone protective agent status at baseline (Yes/No)

Body composition measures of total fat mass (g), total lean mass (g), total body mass (g), fat (%), and lean (%) will also be summarized. Additionally, the ratio of total fat mass divided by total lean mass will be included.

DXA summaries will be presented once including all subjects and visits where the same machine as screening was used, and again including all subjects and visits (regardless of machine switching). The summaries will be provided for both centrally read and locally read results.

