APPENDIX C. RESPONSIBILITIES OF THE INVESTIGATOR

Protocol M20-466: A Randomized, Double-Blind, Placebo-Controlled Study to Evaluate the Safety and Efficacy of ABBV-154 in Subjects with Moderately to Severely Active Rheumatoid Arthritis with Inadequate Response to Biologic and/or Targeted Synthetic Disease-Modifying Anti-Rheumatic Drugs (b/tsDMARDs)

Protocol Date: 12 April 2022

Clinical research studies sponsored by AbbVie are subject to the International Council for Harmonisation of Technical Requirements for Pharmaceuticals for Human Use (ICH) Good Clinical Practices (GCP) and local regulations and guidelines governing the study at the site location. In signing the Investigator Agreement, the investigator is agreeing to the following:

1. Conducting the study in accordance with ICH GCP, the applicable regulatory requirements, current protocol and operations manual, and making changes to a protocol only after notifying AbbVie and the appropriate Institutional Review Board (IRB)/Independent Ethics Committee (IEC), except when necessary to protect the subject from immediate harm.
2. Personally conducting or supervising the described investigation(s).
3. Informing all subjects, or persons used as controls, that the drugs are being used for investigational purposes and complying with the requirements relating to informed consent and ethics committees (e.g., IEC or IRB) review and approval of the protocol and its amendments.
4. Reporting complaints that occur in the course of the investigation(s) to AbbVie.
5. Reading the information in the Investigator's Brochure/safety material provided, including the instructions for use and the potential risks and side effects of the investigational product(s).
6. Informing all associates, colleagues, and employees assisting in the conduct of the study about their obligations in meeting the above commitments.
7. Maintaining adequate and accurate records of the conduct of the study, making those records available for inspection by representatives of AbbVie and/or the appropriate regulatory agency, and retaining all study-related documents until notification from AbbVie.
8. Maintaining records demonstrating that an ethics committee reviewed and approved the initial clinical protocol and all of its amendments.

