Rationale: *To clarify which b/tsDMARDs are acceptable to fulfil the criterion #7 by mechanism of action, including guidance for previous use of investigational drugs. To clarify that b/tsDMARDs*

discontinued due to other reasons unrelated to inadequate response will not be accepted to fulfill eligibility criterion #7.

- Protocol Section 3.1, Objectives, Hypotheses, and Estimands; Protocol Section 7.2, Definition of Analysis Populations: Changed the definition of ITT population from all randomized subjects to all subjects who were randomized and received at least 1 dose of study drug.

Rationale: *To exclude subjects from the ITT analysis if they were not dosed to be consistent with analysis methods used in prior clinical trials, which included all randomized subjects who received at least 1 dose of study drug.*

- Protocol Section 3.1, Objectives, Hypotheses, and Estimands; Protocol Section 7.3, Handling Potential Intercurrent Events for the Primary and Secondary Endpoints: Removed the intercurrent event of confounding medication use for all endpoints.

Rationale: *Medications with potential to affect efficacy are either prohibited through the placebo-controlled period or are required to remain at stable dose (as listed in Protocol Section 5.1, Eligibility Criteria, and Protocol Section 5.3, Prohibited Medications and Therapy). Handling of intercurrent events of confounding medication use was removed to allow comparison to prior clinical trials that did not use this analysis method, as this study will be used to inform future development of ABBV-154.*

- Protocol Section 3.7 Biomarker Research Endpoints; Appendix E, Activity Schedule; Operations Manual Section 2.1, Individual Treatment Period Visit Activities; Section 3.9 Biomarker Research Sampling; Section 4.1 Methods and Timing of Safety Assessment; Appendix 7.3, Synovial Biopsy Procedures: Removed mention of synovial biopsy/joint biopsy.

Rationale: *The Optional Synovial Biopsy Substudy has been removed as it has been determined it will not be possible to enroll enough subjects into the Substudy to achieve scientific goals; without expectation for the data to provide meaningful scientific value it is not appropriate to perform the biopsy procedure on study subjects.*

- Protocol Section 4.1, Overall Study Design and Plan: Added 70-Day Follow-up Period to the description of the overall study design.

Rationale: *To provide clarity surrounding the planned duration of the study.*

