Rationale: *To ensure more robust safety data collection at follow up. To ensure drug washout and assess immunogenicity during drug washout.*

- Operations Manual, Section 3.2, Re-Screening: Added wording "without prior AbbVie approval" regarding re-screening.

Rationale: *To clarify the re-screening process.*

- Operations Manual, Section 3.5, Dual-Energy X-Ray Absorptiometry (DXA) Scan: Added collection of Z-score for evaluation of bone mineral density and instruction that measurements should be obtained from the distal forearm if neither the spine nor either hip are able to be scanned or interpreted. Added a Central Imaging Core Lab for central independent review of

DXA data and modified guidance for image acquisition. Removed performance of BMD and body composition assessment if DXA scan is not available.

Rationale: *To improve the robustness and interpretability of the DXA data collected. Other methods of BMD and body composition assessment are not interchangeable with DXA.*

- Operations Manual Section 3.15 Subject Dosing Diary: Added Operations Manual Section 3.15 Subject dosing diary to inform when the subjects will be dispensed a diary and the process of diary documentation and review.

Rationale: *To inform subjects who opted for home dosing during LTE Period 2 and where locally permitted when they will receive a dosing diary, how they will be trained and how the dosing diary will be reviewed and properly documented.*

- Operations Manual, Section 3.16 Clinical Laboratory Tests, Table 1. Added Follicle Stimulating Hormone to the table to reflect changes in Protocol Section 5.2.

Rationale: *Follicle Stimulating Hormone testing was added to align with addition of language in protocol section 5.2 which permits re-testing of FSH during study conduct.*

- Operations Manual, Section 3.16 Clinical Laboratory Tests, Pregnancy Tests (Serum and Urine): Updated language to align with the Protocol Section 5.2. Added "at investigator discretion Follicle Stimulating Hormone may be retested after the Screening visit."

Rationale: *To align with language in Protocol Section 5.2 Contraception Recommendations which outlines requirements for females to be considered of non-childbearing potential. To align with addition of language in Protocol Section 5.2 which permits re-testing of FSH during study conduct.*

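### SAP 10.6 summarizes DXA bone density and body composition visit by visit, with no within-subject change from screening and no matched subject set

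*SAP*

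**What the plan says.** SAP 10.6 states that DXA "is collected at screening, Week 24, Week 78, Week 134, and Week 182". BMD with its T and Z scores is to be summarized by treatment group at each visit, and also by post-menopausal status and by bone-protective agent use. Body-composition measures are summarized as well. Two versions are planned. In the first, "DXA summaries will be presented once including all subjects and visits where the same machine as screening was used"; the second takes all subjects and visits whatever the machine. Summaries are provided for central and for local reads. The section mentions neither change from screening nor a set of subjects common to the visits being compared.

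The amendment log in Protocol Appendix F records changes to how these data are obtained in the current version ("Protocol Date: 12 April 2022"). For the Operations Manual section on DXA it lists:

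- "Added a Central Imaging Core Lab for central independent review of DXA" data, with modified guidance for image acquisition.
- "measurements should be obtained from the distal" forearm when neither the spine nor either hip can be used.
- "Removed performance of BMD and body composition assessment if DXA scan is not available", with the reason that "Other methods of BMD and body composition assessment are not interchangeable with DXA".

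SAP version 2.0 (17 August 2022) post-dates that protocol, and its version history says details for the DXA analysis were added.

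**The concern.** A bone-safety reader wants to know whether subjects on ABBV-154 lose bone. That is a question about change within a subject. Summaries made separately at screening and at Weeks 24, 78, 134 and 182 answer it only if the same kind of subject contributes at each visit, and nothing in SAP 10.6 ensures this.

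The issue carries weight in this trial. Protocol 2.1 names osteoporosis among the long-term effects of glucocorticoids, and Protocol 2.2 says bone mineral density will be closely monitored. There is no placebo-controlled DXA comparison to fall back on, so the course from screening is the main evidence.

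**Working it through.** The documents state no figure for DXA, so there is none to reproduce. The check compares sections and then sizes the effect under assumptions.

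**1. SAP sections side by side.** SAP 10.3 plans mean change from baseline for selected laboratory variables, with the number of observations, baseline mean, visit mean, standard error and 95% confidence interval. SAP 10.4 plans the same for each vital sign. SAP 10.6 plans none of this for DXA.

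**2. Timing.** Placebo subjects are re-randomized to active drug at Week 12 (SAP 2.3), and the first post-screening DXA is at Week 24. By then former placebo subjects may have had 24 − 12 = 12 weeks of ABBV-154.

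**3. Who remains.** LTE Period 1 ends at Week 12 + 66 = 78, and LTE Period 2 at 78 + 104 = 182. The Week 134 and Week 182 scans therefore fall in LTE Period 2, to which only completers of LTE Period 1 are invited (Protocol synopsis). From Week 30, subjects classed as non-responders stop study drug (Protocol 5.4). Protocol 5.6 encourages them to keep attending, but loss is still likely to be selective.

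**4. The same-machine filter.** A screening scan meets the condition automatically. On a natural reading, a subject who later changes machine stays in the screening summary and leaves the later one. The filter limits device mixing but does not make the subjects equal across visits.

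**5. Size of the composition artefact.** Let r be the share of screened-and-treated subjects with a value at the later visit. Let k be the difference in screening mean, in SD, between those with and without that later value. Suppose no subject truly changes.

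- Screening mean = r × mean(retained) + (1 − r) × mean(lost)
- Later visit mean = mean(retained)
- Apparent change = (1 − r) × [mean(retained) − mean(lost)] = (1 − r) × k SD

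For example, r = 0.8 and k = 0.5 give 0.2 × 0.5 = 0.10 SD. Both r and k are assumed:

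| r | k = 0.1 | k = 0.25 | k = 0.5 |
|---|---|---|---|
| 0.9 | 0.01 | 0.025 | 0.05 |
| 0.8 | 0.02 | 0.05 | 0.10 |
| 0.7 | 0.03 | 0.075 | 0.15 |
| 0.5 | 0.05 | 0.125 | 0.25 |

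The sign follows the sign of k, so the artefact can imitate a loss or hide one. In a paired summary both means come from the same subjects, and this artefact is exactly 0 within them.

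**6. Precision.** With n subjects at both visits, equal SDs and within-subject correlation ρ, the standard error of change is SD × √(2(1 − ρ)/n) when paired. It is SD × √(2/n) if the visits are treated as independent. The ratio is 1/√(1 − ρ): 2.2, 3.2, 4.5 and 7.1 for assumed ρ of 0.80, 0.90, 0.95 and 0.98. A reader working from separate visit summaries would lose that precision.

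**The case against.** The strongest reply is that SAP 10.6 already contains real safeguards and that these are descriptive safety tables.

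- A reader might infer that central and local reads are mixed. The text does not support this: it provides summaries for both read types, most naturally as separate tables. What stays open is whether scans taken before the core lab was added will be read centrally. If not, those subjects have no screening value in the central-read table.
- A reader might infer that other measurement methods are pooled with DXA. SAP 10.6 speaks of DXA measurements, which on a plain reading excludes non-DXA BMD. The documents do not show that any non-DXA value exists. The gap is the lack of an explicit rule, mainly for body composition, where the sentence does not repeat the word DXA.
- A reader might try to calculate how many scans pre-date the change. No first-subject date or accrual rate is given. The remark that "it has been determined it will not be possible to enroll enough subjects into the Substudy to" reach its goals fits a trial already recruiting, but it is a forecast and dates nothing.
- A reader might conclude that an artefact as large as a drug effect could arise. The documents give neither a BMD effect nor a BMD SD, so this cannot be shown.
- Randomization was concurrent, so calendar changes in reading should fall similarly on all dose groups. The artefact cancels between groups when r and k are equal. It does not cancel under differential loss: r = 0.8 against 0.7 at k = 0.25 leaves 0.075 − 0.05 = 0.025 SD.
- DXA is not named among the safety endpoints in Protocol 3.5 or SAP 3.4, and no test is planned. Some handling rules may sit in the Operations Manual or core-lab documents, which were not available.

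These points narrow the concern to trends from screening. They do not supply the missing change summary.

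**Conclusion.** The point holds as a gap in SAP 10.6. DXA is summarized by visit only, without the change-from-baseline approach that the SAP uses for laboratory and vital-sign data. With no placebo-controlled DXA visit and a selected population at later visits, differences between visit summaries can reflect who was scanned rather than bone change. The same-machine version reduces one source of error and leaves this one.

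The size is modest when follow-up is good (0.01 to 0.05 SD at 90%) and grows with loss (0.05 to 0.25 SD at 50%). These figures rest on assumed follow-up shares and on an assumed screening difference of 0.1 to 0.5 SD between subjects with and without follow-up; they are not estimates for this trial. The lack of a change summary and of a matched set can be read directly from the text and needs no assumption. The SAP should be amended, but no efficacy conclusion depends on it.

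**What to change.** Keep the existing summaries and add to SAP 10.6:

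1. Change from screening at Weeks 24, 78, 134 and 182, in subjects with both values from DXA on the same machine, at the same skeletal site and with the same read type. Central-central pairs form the main table and local-local pairs the support. The site condition is needed because of the forearm fallback.
2. Absolute change for T scores, Z scores and percentages; absolute and percent change for BMD and the mass measures. Percent change does not suit T and Z scores, which can be zero or negative.
3. N and the screening mean of those same subjects at each visit.
4. A statement that any non-DXA values obtained before the amendment are excluded from the BMD and body-composition tables.
5. A statement on whether scans taken before the amendment are read centrally.

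The cost is SAP wording and table shells. The downside is fewer subjects in the paired tables. Pairing also does not make those who remain representative of everyone randomized, which is why the existing summaries should stay beside them.
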